10 REPORTING ADVERSE EVENTS

10.1 Safety Parameters and Definitions

Safety assessments will consist of monitoring and recording protocol-defined AEs and SAEs; measurement of protocol-specified hematology, clinical chemistry, and urinalysis variables; measurement of protocol-specified vital signs; and other protocol-defined events of special interest that are deemed critical to the safety evaluation of the study drug.

10.1.1 Adverse Events

For this protocol, an adverse event (AE) is any untoward medical occurrence in a subject, temporally associated with the use of study intervention, whether or not considered related to the study intervention.

An AE can therefore be any unfavorable and unintended sign (including an abnormal laboratory finding), symptom, or disease (new or exacerbated) temporally associated with the use of study intervention.

Events meeting the AE definition include:

- Exacerbation of a chronic or intermittent pre-existing condition including either an increase in frequency and/or intensity of the condition.
- New conditions detected or diagnosed after study intervention administration even though it may have been present before the start of the study.
- Signs, symptoms, or the clinical sequelae of a suspected drug-drug interaction.

Events not meeting the AE definition include:

- Any clinically significant abnormal laboratory findings or other abnormal safety assessments which are associated with the underlying disease, unless judged by the investigator to be more severe than expected for the subject's condition.
- The disease/disorder being studied or expected progression, signs, or symptoms of the disease/disorder being studied, unless more severe than expected for the subject's condition.
- Medical or surgical procedure (eg, endoscopy, appendectomy): the condition that leads to the procedure is the AE.
- Situations in which an untoward medical occurrence did not occur (social and/or convenience admission to a hospital).
- Anticipated day-to-day fluctuations of pre-existing disease(s) or condition(s) present
 or detected at the start of the study that do not worsen.

10.1.1.1 Bleeding and Suspected Bleeding Events

All bleeding events and suspected bleeding events, regardless of the need for exogenous FVIII therapy as treatment, should be captured in subject diaries and recorded on the designated bleeding eCRF. Bleeding events and suspected bleeding events should not be reported as adverse events, with the following exception:

All bleeding events and suspected bleeding events which meet one or more of the
criteria for being serious (refer to Section 10.2) should be reported as serious adverse
events (whether or not they are bleeding events that are normal sequelae of
hemophilia, and whether or not they required exogenous FVIII as treatment).

10.2 Serious Adverse Events

A serious adverse event (SAE) is any untoward medical occurrence that, at any dose:

- Results in death
- Is life-threatening

Note: Life-threatening refers to an event in which the subject was at risk of death at the time of the event. It does not refer to an event, which hypothetically might have caused death, if it were more severe.

Requires inpatient hospitalization or prolongation of existing hospitalization
 Note: In general, hospitalization signifies that the subject has been detained (usually involving at least an overnight stay) at the hospital or emergency ward for observation and/or treatment that would not have been appropriate in the physician's office or outpatient setting. If the investigational product preparation, infusion, and post-infusion observation period require transfer to an inpatient setting for completion, in the absence of an AE, this will not be considered an SAE.

Complications that occur during hospitalization are AEs. If a complication prolongs hospitalization, the event is serious.

Hospitalization for elective treatment of a pre-existing condition that did not worsen from baseline is not considered an AE.

- Results in persistent or significant disability or incapacity
- Is a congenital anomaly or birth defect in the child or fetus of a subject exposed to IP prior to conception or during pregnancy
- Is an important medical event or reaction that, based on medical judgment, may jeopardize the subject or require medical/surgical intervention to prevent one of the other outcomes listed above (eg, anaphylaxis)

10.2.1 Events of Special Interest (EOSI)

The following EOSI need to be reported to the Sponsor within 24 hours of site awareness, irrespective of seriousness, severity or causality:

- Elevation of ALT > ULN or $\geq 1.5x$ baseline value, regardless of whether that elevation triggers an initiation or modification of oral corticosteroid treatment
- Events potentially meeting the criteria for Hy's law (ALT or AST elevation $\geq 3x$ ULN plus total bilirubin $\geq 2x$ ULN)
- Thromboembolic event
- Systemic hypersensitivity, anaphylactic, or anaphylactoid reactions (refer to Appendix 1)
- Development of anti-FVIII inhibitory antibodies (inhibitors)
- Any new diagnosis of malignancy (except non-melanoma skin cancer)

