9.3.2 Exclusion Criteria

Individuals who meet any of the following exclusion criteria will not be eligible to participate in the study:

- 1. Detectable pre-existing antibodies to the AAV5 capsid.
- 2. Any evidence of active infection or any immunosuppressive disorder, including HIV infection.
- 3. Significant liver dysfunction with any of the following abnormal laboratory results:
 - ALT (alanine aminotransferase) > 1.25x ULN;
 - AST (aspartate aminotransferase) > 1.25x ULN;
 - GGT (gamma-glutamyltransferase) > 1.25x ULN;
 - Total bilirubin > 1.25x ULN;
 - Alkaline phosphatase > 1.25x ULN; or
 - INR (international normalized ratio) ≥ 1.4.

Subjects whose liver laboratory assessments fall outside of these ranges may undergo repeat testing of the entire liver test panel within the same Screening window and, if eligibility criteria are met on retest, may be enrolled after confirmation by the Medical Monitor.

- 4. Prior liver biopsy showing significant fibrosis of 3 or 4 as rated on a scale of 0.4 on the Batts-Ludwig (Batts 1995) or METAVIR (Bedossa 1996) scoring systems, or an equivalent grade of fibrosis if an alternative scale is used.
- 5. Evidence of any bleeding disorder not related to hemophilia A.
- 6. Platelet count of $< 100 \times 10^9/L$.
- 7. Creatinine $\geq 1.5 \text{ mg/dL}$.
- **8.** Liver cirrhosis of any etiology as assessed by liver ultrasound.
- Chronic or active hepatitis B as evidenced by positive serology testing (HBsAg, HBsAb, and HBcAb) and confirmatory HBV DNA testing. Refer to the Centers for Disease Control (CDC) table for the interpretation of serological test results in the Laboratory Manual.
- **10.** Active Hepatitis C as evidenced by detectable HCV RNA or currently on antiviral therapy.
- 11. Active malignancy, except non-melanoma skin cancer.
- 12. History of hepatic malignancy.
- 13. History of arterial or venous thromboembolic events (eg, deep vein thrombosis, non-hemorrhagic stroke, pulmonary embolism, myocardial infarction, arterial embolus), with the exception of catheter-associated thrombosis for which anti-thrombotic treatment is not currently ongoing.
- 14. Known inherited or acquired thrombophilia, including conditions associated with increased thromboembolic risk, such as atrial fibrillation.

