9.4.8.1 Concomitant Hemophilia Treatments

Subjects on prophylactic FVIII therapy will discontinue their regular treatment regimen starting 4 weeks after the day of infusion and switch to an "episodic" schedule. FVIII replacement therapy can always be taken as needed by the subject for treatment of an acute bleeding episode; the subject must carefully record his treatment and bleeding episodes in his

diary. Prophylactic FVIII use can be used on a case-by-case basis and in consultation with the Medical Monitor to prevent bleeding in extenuating circumstances (eg, peri-operative).

In addition, information on FVIII usage and bleeding episodes by medical history must be well-documented and available and will be collected from subjects for the 12-month period immediately preceding study enrollment. Further information on the details that should be provided as part of the subject's well-documented medical and FVIII usage history are provided in the On Site File Binder.

In order to enable rigorous comparisons of pre-study versus on-study FVIII usage and bleeding episodes, the Medical Monitor will review each screened patient's prior bleed and hemophilia medication logs to determine if they are of "high-quality". Elements that will be assessed to judge the quality of such historical data may include, but are not limited to, the following:

- Date, type (eg, joint, muscle, other), location of bleeds
- Date, name, dose (calculated in IU/kg), and reason for use (eg, usual prophylaxis, one-time prophylaxis, treatment for bleed, surgery) of hemophilia medications.

9.4.8.2 Reactive Glucocorticoid Treatment and/or Immunosuppressive Agent Treatment of Elevated Hepatic Transaminases

Refer to corticosteroid prescription guidelines for recommended monitoring for, and management of, potential side effects of corticosteroids, including guidance on medications that should be avoided during corticosteroid treatment.

Reactive oral corticosteroids (prednisone or converted equivalent) should be initiated when either of the following occurs post-BMN 270 infusion in any subject and after consultation with the Medical Monitor (or their designee):

- ALT > ULN or ≥ 1.5x baseline value in 2 consecutive assessments within 72 hours and alternative etiologies have been ruled out, or ALT ≥ 3x ULN in 2 consecutive assessments within 48 hours (refer to Table 9.4.8.2.1)

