 - Whenever possible, a confirmatory lab draw for ALT should be performed, along with FVIII activity, prior to initiating reactive oral corticosteroids.
 - Corticosteroids may be delayed if elevations in ALT are clearly not related to BMN 270 (eg, elevated ALT with concurrent increase in CPK due to intensive exercise), although this should be discussed with the Medical Monitor (in particular for elevations occurring more than 52 weeks after BMN 270 dosing).

270-301 Amendment 7 (United States Specific)

Page 73

 Alternative immunosuppressive agents may also be considered for use on a case-by-case basis and following consultation with the Medical Monitor (eg, if prolonged corticosteroid use is contraindicated).

Unless otherwise indicated, reactive corticosteroid treatment should be initiated at a dose of 60 mg/day. If the ALT level remains stable or declines after 2 weeks, consider gradual taper of corticosteroids: 40 mg/day for 3 weeks, 30 mg/day for 1 week, 20 mg/day for 1 week and 10 mg/day for 1 week. Should a scenario arise in which differences from the minimum recommended dose and/or duration of reactive corticosteroids may be clinically indicated, a discussion should take place between the Investigator and Medical Monitor regarding corticosteroid dose adjustments. Management of ALT elevations with reactive corticosteroids, including tapering of doses and managing worsening and/or recurrent ALT elevations, should be guided by the following (Table 9.4.8.2.1):

Page **74**

Table 9.4.8.2.1: Management of ALT Elevations with Reactive Corticosteroids

	
ALT ≥ 1.5x Baseline or > ULN	 Repeat LTs and FVIII within 24-72 hours Continue to monitor LTs until ALT is stable or not increasing Investigate for alternative etiologies (eg, concomitant medications, viral or autoimmune hepatitis, alcohol use, recreational drug use, special diets, strenuous exercise, prior and/or concurrent illnesses, exposure to environmental and/or industrial chemicals, etc.) If no alternative etiology is found, initiate reactive corticosteroids with the following tapering schedule: 60 mg x 2 weeks; 40 mg x 3 weeks; 30 mg x 1 week; 20 mg x 1 week; 10 mg x 1 week upon consultation with the Medical Monitor

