9.7.8.4 Liver and Hepatitis Testing

Subjects will be screened for evidence of previous or active hepatitis B or hepatitis C infection at Screening; hepatitis B screening should include HBsAg, HBsAb, and HBcAb. Subjects with documented results showing an absence of active hepatitis B or hepatitis C infection (as measured by positive DNA for hepatitis B or positive RNA testing for hepatitis C) 30 days prior to providing signed informed consent do not need to repeat those tests during the screening period.

Evidence of ongoing hepatitis B or hepatitis C infection is exclusionary. Subjects with a history of hepatitis B or hepatitis C infection prior to study entry will be tested for hepatitis B and hepatitis C reactivation at Week 16. Subjects with a history of hepatitis B or hepatitis C will be asked for information about the treatments received as part of their medical history assessment at Screening.

Subjects with a previous history of hepatitis B or hepatitis C who receive therapeutic oral corticosteroids prior to Week 16 do not need to complete the Week 16 reactivation assessment; instead, they will be tested for hepatitis B and hepatitis C reactivation at the time points listed in Table 9.1.6.

A liver ultrasound and liver tests (LTs) during Screening will identify any significant hepatic dysfunction.

LTs will be monitored on a regular basis; at each time point, the following LTs should be assessed:

Table 9.7.8.4.1: Liver Tests

Liver Tests (LTs)			
Alkaline Phosphatase	AST (SGOT)	Total Bilirubin	LDH
ALT (SGPT)	Direct Bilirubin	GGT	

ALT, alanine aminotransferase; AST, aspartate aminotransferase; GGT, gamma glutamyltransferase; LDH, lactate dehydrogenase; SGOT, serum glutamic oxaloacetic transaminase; SGPT, serum glutamic pyruvic transaminase

Elevated ALT levels (above the upper limit of normal range) should be evaluated according to the plan outlined in Table 9.4.8.2.1 (note that these evaluations may indicate additional testing of LTs and FVIII levels at unscheduled visits; these unscheduled laboratory tests may

be completed by a mobile nursing professional at sites where the use of MN services has **been approved**).

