10.4.1.4 Abnormal Laboratory Values

Laboratory test results will be recorded on the laboratory results pages of the eCRF, or appear on electronically produced laboratory reports submitted directly from the central laboratory, if applicable.

Any laboratory result abnormality fulfilling the criteria for a SAE or EOSI should be reported as such, and recorded in the AE eCRF.

Any laboratory result abnormality of CTCAE Grade 4 or 5 should be recorded as an SAE in the AE eCRF.

A clinical laboratory abnormality is considered clinically significant and should be documented as an AE if not refuted by a repeat test to confirm the abnormality and **any** one or more of the following conditions is met:

- Accompanied by clinical symptoms
- Requiring a change in concomitant therapy (eg, addition of, interruption of, discontinuation of, or any other change in a concomitant medication, therapy or treatment).
- The abnormality suggests a disease and/or organ toxicity
- The abnormality is of a degree that requires active management (eg, change of dose, discontinuation of study drug, more frequent follow-up assessments, further diagnostic investigation, etc.)

This applies to any protocol and non-protocol specified safety and efficacy laboratory result from tests performed after the first dose of study medication that falls outside the laboratory reference range and meets the clinical significance criteria.

This does not apply to any abnormal laboratory result that falls outside the laboratory reference range but that does not meet the clinical significance criteria (these will be analyzed and reported as laboratory abnormalities), those that are considered AEs of the type explicitly exempted by the protocol, or those which are a result of an AE that has already been reported.

For purposes of this study, laboratory tests showing a decreased level of FVIII activity should not be reported as adverse events unless there is an impact to clinical outcomes (eg, increased rate of bleeding, worsening of joint disease).

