10.4.1.5 Pre-existing Conditions

A pre-existing condition is one that is present prior to administration of BMN 270. Such conditions should be recorded as medical history on the appropriate eCRF.

A pre-existing condition should be recorded as an AE or SAE during the study only if the frequency, intensity, or character of the condition worsens during the study period. It is important to convey the concept that a pre-existing condition has changed by including applicable language in the verbatim description of the event (eg, more frequent headaches).

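### Entry allows ALT up to 1.25x ULN but the ALT event of special interest needs only ALT > ULN, so its reported incidence can include subjects whose ALT did not rise

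*Protocol*

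**What the plan says.** All references are to the Protocol, Amendment 7 (United States).

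- **Entry.** Exclusion criterion 3 (Section 9.3.2, repeated in the Synopsis) removes a candidate with "ALT (alanine aminotransferase) > 1.25x ULN". A value above ULN and up to 1.25x ULN is eligible.
- **Event.** Section 10.2.1 lists "Elevation of ALT > ULN or $\geq 1.5x$ baseline value, regardless of whether that elevation triggers" a start of, or change in, oral corticosteroids. It goes to the sponsor within 24 hours whatever its seriousness, severity or cause.
- **Recording.** Section 10.4.1.4: "Any laboratory result abnormality fulfilling the criteria for a SAE or EOSI should be reported" as such and entered on the AE eCRF. Section 10.4.1.5: "A pre-existing condition should be recorded as an AE or SAE during the study only if the" condition gets worse in frequency, intensity or character. Section 10.1.1 likewise leaves out expected fluctuation in conditions already present at study start that have not worsened.
- **Corticosteroid trigger.** Section 9.4.8.2 uses the same two ALT limbs: "ALT > ULN or ≥ 1.5x baseline value in 2 consecutive assessments within 72 hours and alternative etiologies have been ruled out", with Medical Monitor consultation. The first row of Table 9.4.8.2.1 repeats the limbs.

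No section gives a separate rule for a subject whose baseline ALT was already above ULN.

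**The concern.** The event is meant to pick up ALT elevation after BMN 270. For a subject admitted above ULN, the first limb is already satisfied before dosing, so the event can reflect the entry criterion rather than anything that followed the infusion. This study has one arm and each subject is his own control (Section 9.2), so no comparison group would cancel such cases out.

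Sites also face two instructions for the same number. The sentence on EOSI values sends it to the AE form; the sections on pre-existing conditions keep it off. Sites that resolve this differently will produce AE counts that differ for reasons unrelated to the product. Section 7.4 reports ALT elevation in most treated subjects, so this is a safety finding readers will look at closely.

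**Working it through.** The plan gives no figure that depends on this definition, so there is nothing to reproduce. The rule can be checked directly in units of ULN.

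**Inputs.** Let b be baseline ALT divided by ULN and x the post-infusion ALT divided by ULN.

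- Eligible: b ≤ 1.25 (Section 9.3.2).
- Event: x > 1 or x ≥ 1.5b (Section 10.2.1).

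**Step 1, unchanged ALT.** Put x = b. The second limb needs b ≥ 1.5b, which is impossible. The first needs b > 1. Every eligible baseline in (1.0, 1.25] therefore meets the event with no change.

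**Step 2, smallest change that meets the event.** The post/baseline ratio must exceed 1/b or reach 1.5, whichever comes first.

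| Baseline b (x ULN) | Ratio needed | Reading |
|---|---|---|
| 2/3 or lower | 1.5 | 50% rise |
| 0.80 | above 1/0.80 = 1.25 | rise above 25% |
| 1.00 | above 1.00 | any rise |
| 1.10 | above 1/1.10 = 0.909 | met after a fall of up to about 9% |
| 1.20 | above 1/1.20 = 0.833 | met after a fall of up to about 16.7% |
| 1.25 | above 1/1.25 = 0.800 | met after a fall of just under 20% |

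Above two thirds of ULN the ULN limb is always reached first (1.5 × 2/3 = 1).

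**Step 3, the recording rules side by side.** Take b = 1.20 and x = 1.20 after infusion. Under 10.2.1 it is an EOSI. Under 10.4.1.4 it is therefore recorded on the AE eCRF. Under 10.4.1.5 and 10.1.1 it has not worsened, so it is not an AE. A site cannot follow all of these as written.

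**Step 4, the corticosteroid trigger.** Two unchanged values at b = 1.20 within 72 hours satisfy the ALT limb in 9.4.8.2. The other conditions, a search for alternative causes and Medical Monitor consultation, do not refer to baseline ALT.

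**Step 5, size.** The protocol does not give the distribution of baseline ALT. With about 130 subjects planned, each subject counted only because of his entry value adds 1/130 = 0.77 percentage points to incidence. The total is at most 0.77 times the number who entered above ULN, and less if some of them later had a true rise.

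**The case against.** **It is a surveillance net.** Section 10.2.1 is a list for rapid notification, deliberately sensitive and independent of causality. An entry ceiling and a monitoring threshold serve different purposes and may overlap. This stands, and it is why the 24-hour threshold should be left alone. It does not settle what the AE tables then count.

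**Elevation implies a rise.** The text does not support this. Section 9.7.8.4 describes elevation by level: "Elevated ALT levels (above the upper limit of normal range) should be evaluated according" to Table 9.4.8.2.1.

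**The recording conflict is narrow.** Two sections state the non-worsening rule, and the exemptions at the end of 10.4.1.4 cover AE types the protocol exempts elsewhere. A careful site might read those as reaching this case. They are attached to the clinical-significance test, however, and do not mention values present at baseline, so the ambiguity remains.

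Several stronger readings are tempting, and the document does not support them:

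- *Subjects with unchanged ALT would be put on corticosteroids automatically.* No. The table says "If no alternative etiology is found, initiate reactive corticosteroids with the following tapering schedule", initiation follows Medical Monitor consultation, and delay is allowed when the elevation is clearly unrelated to BMN 270.
- *Onset would be fixed at the first sample and the event might never resolve.* No such onset rule appears, and Section 10.6 lets follow-up end once an event has stabilised.
- *A planned comparison of ALT onset or duration with Study 270-201 would be biased.* That comparison is background in Section 7.4. Sections 14.7 and 25.3.6 plan no ALT onset or duration analysis.
- *Section 9.7.8.4 contradicts the table.* It sends values above ULN to a table that also has a baseline-relative entry route; the two are compatible.
- *The 1.5x-baseline limb is faulty because it can fire inside the normal range.* That is how a baseline-relative limb works, and it is a design choice.

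**Conclusion.** The overlap is certain on the text: an eligible subject with baseline ALT in (1.0, 1.25]x ULN meets the ALT event with no rise, and at 1.25x ULN after a fall of just under 20%. The recording sections then disagree on whether that value belongs on the AE form. ALT-elevation incidence can therefore include subjects with no post-infusion change. The ALT limb of the corticosteroid trigger is also met without change, although initiation is not automatic.

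The size is unknown and may be small, because the number who entered above ULN is not stated. The conclusion assumes that at least one treated subject had such a baseline and that sites apply 10.2.1 and 10.4.1.4 as written. No efficacy endpoint or type I error rate is affected. This should be corrected, but it does not undermine the study.

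A reader might infer that the event should move to 1.5x baseline for subjects who entered above ULN. That does not follow. At b = 1.25 the reporting level would become 1.5 × 1.25 = 1.875x ULN, which would set a clinical threshold and loosen expedited reporting for those with the highest entry ALT.

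**What to change.** 1. Leave the 24-hour reporting threshold in 10.2.1 as it is.
2. In the safety tables, count an ALT-elevation event as post-infusion only when the value exceeds the subject's own baseline. Show separately the subjects with baseline ALT above ULN whose values did not worsen. For a baseline at or below ULN this changes nothing, since any value meeting either limb already exceeds baseline.
3. Make 10.4.1.4 consistent with 10.1.1 and 10.4.1.5 for values that were present at baseline and have not worsened.
4. The sponsor must reconcile the entry ceiling in 9.3.2 with the ALT limb in 10.2.1, 9.4.8.2 and Table 9.4.8.2.1. No threshold is proposed here.

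**Cost.** One extra table row, one clarifying sentence in 10.4.1.4, and a slightly lower reported ALT-event count. Liver tests are already collected before infusion (Table 9.1.1). Because the reporting definition stays the same, events already reported keep their meaning, and the tables can be made this way for the 2-year analysis, with its cutoff around 15 November 2021.

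**Limit.** The rule removes values at or below baseline but still counts small upward fluctuations, which are likely to occur with weekly liver tests to Week 36. Stating how many subjects entered above ULN lets a reader bound what remains.
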